**Figure 1: Teachable Moment Model**

interpretation of the event (e.g., significance, cause, meaning) determines subsequent behavior change. Based on this, McBride and Ostroff [11] indicated that a TM (Figure 1): (1) increases perception of personal risk and outcome expectancies, (2) prompts a strong affective or emotional response, and (3) redefines self-concept or social role [5]. Consistent with this conceptualization, Gritz et al. [21] followed 840 lung cancer patients and found that 83.2% quit smoking at the time of diagnosis. According to the TMM, a smoker diagnosed with cancer likely has reactions such as, “if I continue smoking I will probably reduce my chances of surviving” (risk perception), “I feel very guilty and afraid when I light up a cigarette” (emotional response), and “what is everybody going to think if I continue smoking after getting cancer?” (self-concept/ social role). These or similar reactions influence an individuals’ motivation that will directly impact their smoking cessation. However, patients with cancers not widely known to be associated with smoking may have lower perceptions of risk, less smoking-related emotion response, and less redefinition of their self-concept and social role regarding smoking. So, as a consequence of the differences in the link to smoking by cancer type, the TM may not be operating equivocally across cancer types. **Therefore, in the present project we will address each of the three constructs of the TMM to increase smoking cessation motivation in patients with a cancer not widely known to be associated with smoking.** We will focus on breast, colorectal, gynecological, skin melanoma, and bladder cancers. Two of these are not currently considered smoking related (e.g., breast and skin melanoma) and three have sufficient evidence to support a causal role of smoking (e.g., colorectal, gynecological, and bladder) [1]. These cancers have high prevalence in the population, they usually have high rates of smoking, and most have a better long-term prognosis compared to other types of cancer (e.g., pancreas, liver). Thus, a wide range of the cancer population could benefit from this intervention. If successful, it could be extended to all types of cancer in the future, including lung or H&N cancer patients with low cessation motivation. Although the ultimate goal is smoking cessation, this project addresses an important first step toward that goal—motivation to quit smoking.

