For the assessment of **affective and emotional response**, we will use the International Positive and Negative Affect Schedule Short Form (I-PANAS-SF) [57] and the Fears of Cancer Relapse/Recurrence (FAC) scale [58] and one item created ad hoc for assessing the role of smoking in cancer relapse. The PANAS assess positive and negative affect and the FAC assesses beliefs and anxieties about possible cancer recurrence [58]. In the absence of a validated measure of **self-image**, we will create a questionnaire to assess how patients perceive themselves as a patient now and in the future following the conceptualization proposed by Hoyle and Sherrill [59] of the role played by possible selves in motivation and behavior change.

**Motivation.** The Contemplation Ladder [60] will be the

primary measure of motivation. It is a valid measure for the assessment of readiness to quit smoking [60] and has been used previously with cancer patients [61]. The Stages of Change Algorithm (SOC) [62], is also widely used and has been used with cancer patients [14, 56]. Finally, we will use the short form of the smoking abstinence-related

motivational engagement (ARME), which is a valid and reliable measure of cessation motivation that includes items related to the smokers' daily experience (e.g., "I spend a great deal of time thinking about becoming or staying smoke-free."), and four global items to assess abstinence motivation: "I am committed to being smoke-free;" "It is important for me to be a non-smoker;" "I want to become or stay smoke-free;" and "I am devoted to being smoke-free" [66].

Table 2. Timing of Assessments for Aim 2

	Baseline	Post-motivation intervention	1 month follow-up
Demographic and cancer information	✓		
Tobacco measures	✓	✓	✓
Perception of smoking relatedness	✓	✓	✓
Teachable Moment measures	✓	✓	✓
Motivation	✓	✓	✓
Treatment Satisfaction		✓	

**Treatment satisfaction.** Treatment satisfaction and acceptability of the intervention will be assessed using items based on the Client Satisfaction Questionnaire (CSQ) [63]. This is a standard measure used across health care delivery, including smoking cessation self-help interventions [23, 26].

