### **F.8. Statistical Design and Power**

We expect to include a total of 50 cancer patients (10 per cancer site) in this study. Assuming follow-up of 80% of enrolled participants across the 5 cancer sites, 2-tailed  $\alpha$  of .05, and power ( $1-\beta$ ) of .80, this study will be powered to detect a small-medium effect size ( $f$ ) of .20.

Acceptability and feasibility will be evaluated using descriptive statistics. For acceptability we will assess patients' treatment satisfaction through the mean scores of a questionnaire based on the CSQ and open-ended feedback from participants. This questionnaire will also inform about how many participants read the intervention materials, which will be used as an indicator of demand (criterion:  $\geq 80\%$  of participants enrolled in Study II). Feasibility will be measured by the number of patients meeting inclusion criteria to participate in the study, agreement to participate in the study ( $\geq 75\%$  of those meeting inclusion criteria and approached to participate), percentage of participants completing baseline assessment measures ( $\geq 85\%$  of those who agree to participate in the study), and percentage of participants completing the one week and one-month follow-up assessment ( $\geq 80\%$  of those who completed baseline). Changes in cessation motivation and Teachable Moment Model variables will be assessed using repeated-measures Analysis of Variance (ANOVA). Finally, we will receive data from MCC's TTSSs on whether participants followed through with referrals to them and we will capture basic website analytics. These will serve as behavioral indicators of cessation motivation.

Other collected variables will also be examined on an exploratory basis. For example, sex differences will be analyzed, as will differences between cancers typically affecting women (gynecological, breast) versus men (bladder).

The pilot study will not include a control group, nor be powered to test moderator or mediator variables. However, results will inform on the feasibility and scope of a potential, subsequent RCT.

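### Two of the three Teachable Moment elements are measured mainly without reference to smoking, so the F.8 change test is poorly aimed at the shift that B.4 argues for

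*Combined protocol and SAP*

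**What the plan says.** **Model and rationale (B.4).** The numbered constructs are general: a teachable moment "prompts a strong affective or emotional response, and (3) redefines self-concept or social role". The illustrations are about smoking. Emotional response is "I feel very guilty and afraid when I light up a cigarette", and self-concept or social role is "what is everybody going to think if I continue smoking after getting cancer". The argument for intervening in these cancers is that such patients may have "less smoking-related emotion response, and less redefinition of their self-concept and social role regarding smoking". B.4 then commits the project to address all three constructs.

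**Measures (D.2.3).**
- Perceived risk uses the POR questionnaire, whose subject is the effect of continued smoking on cancer.
- Emotional response uses two scales: "The PANAS assess positive and negative affect and the FAC assesses beliefs and anxieties about possible cancer recurrence". To these is added "one item created ad hoc for assessing the role of smoking in cancer relapse".
- For self-image, in the absence of a validated measure, "we will create a questionnaire to assess how patients perceive themselves as a patient now and in the future", following a possible-selves account of motivation and behavior change.

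**Analysis (F.8).** "Changes in cessation motivation and Teachable Moment Model variables will be assessed using repeated-measures Analysis of Variance (ANOVA". F.8 also says that there is no control group. Table 2 places the Teachable Moment measures at baseline, one week and one month. No section says which emotional measure is the test variable, how the ad hoc item is scored, or that change is adjusted for treatment phase or time since diagnosis.

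**The concern.** The booklet is meant to change how a patient feels about smoking after diagnosis and how she sees herself as someone who smokes. Two of the three measured elements mostly ask something else. A patient may come to see herself as a non-smoker while her view of herself as a patient stays put. Her mood, her fear of recurrence and her view of herself as a patient may also move with treatment or prognosis while her feelings about smoking do not. Entry is within six months of diagnosis (F.1.1), when such movement is plausible.

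At stake is what the change tests can say about mechanism before a larger trial. A flat result on these two elements would be hard to read, because the measures may not have been looking at the smoking-related shift. A positive result would be more open than it need be to explanation by the cancer's course.

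**Working it through.** **Step 1. Element by element.**

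| Element | Deficit argued in B.4 | Measure in D.2.3 | Refers to smoking? |
|---|---|---|---|
| Perceived risk | Lower perceived risk | POR | Yes |
| Emotional response | Weaker smoking-related emotion | I-PANAS-SF, FAC, one ad hoc item | Only the ad hoc item, which asks about smoking's role in relapse and so reads as a belief, not a feeling |
| Self-concept / social role | Weaker redefinition regarding smoking | Questionnaire to be written on the self as a patient | Not stated |

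The match between argument and measure is good for one element and loose for two.

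**Step 2. Reproduce the plan's own figure.** F.8 states that f = .20 is detectable with 80% power at two-sided alpha .05 and 80% follow-up.
- Analysed: N = 50 × 0.80 = 40.
- Assessments: m = 3 (D.2.3).
- Correlation between assessments: not given; rho = 0.5 assumed.
- Within-subject time effect, one group, sphericity: lambda = f² × N × m / (1 − rho) = 0.04 × 40 × 3 / 0.5 = 9.6, with df1 = m − 1 = 2 and df2 = (N − 1)(m − 1) = 39 × 2 = 78.
- Power from the noncentral F is 0.782, and the f detectable at 80% power is 0.204, which rounds to the plan's figure.
- The detectable f depends on rho: 0.289 at rho = 0, 0.242 at 0.3, 0.183 at 0.6 and 0.158 at 0.7.

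**Step 3. Illustrate a missed shift.** Suppose the booklet moves the smoking-specific element by f = .20 and the scale carries only a share of it. With N = 40, m = 3 and rho = 0.5, lambda = 240 × f².

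| Share carried (assumed) | Visible f | lambda | Power | N analysed for 80% power |
|---|---|---|---|---|
| 100% | .20 | 9.6 | 0.782 | 42 |
| 75% | .15 | 5.4 | 0.520 | 73 |
| 50% | .10 | 2.4 | 0.255 | 163 |
| 25% | .05 | 0.6 | 0.096 | 644 |

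**Step 4. Illustrate drift.** An uncontrolled time effect looks the same whatever causes it, so the same formula applies. If the booklet does nothing but affect or recurrence fear drifts, the chance of a significant result is 0.096 at a drift of f = .05, 0.255 at .10, 0.520 at .15 and 0.782 at .20, against a nominal .05.

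**Step 5. What these figures are not.** The shares and drifts are assumed; the documents give none. New smoking-specific items would not carry 100% either, since they would be few and unvalidated. Steps 3 and 4 therefore show the direction and shape of the problem, not its size in this trial.

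**The case against.** A reader might infer that B.4 defines the two elements as smoking-specific and that D.2.3 therefore measures the wrong constructs. The documents do not support that. The constructs are worded generally both in the Specific Aims and in B.4's numbered list. The event in question is the cancer diagnosis, so affect and fear of recurrence are responses the model can cover. The smoking reference lies in the examples and in the rationale sentence.

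The booklet's own targets are also mixed. Phase 2 of D.2.1 plans disease-specific vignettes for emotion, and for self-concept it plans to discuss life and social changes tied to the cancer type as well as to quitting. A questionnaire on the self as a patient matches part of that. It is unwritten and rests on a possible-selves approach to behavior change, so nothing excludes smoking content.

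Other smoking-specific measures are taken at all three assessments: perceived risk, perceived smoking-relatedness, the Contemplation Ladder and the ARME items. One ARME item is about the importance of being a non-smoker, so a shift of that kind would not go wholly unseen.

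The consequence is limited too. D.2.2 treats these changes as preliminary efficacy, and D.2.7 rests the next trial on demand, feasibility and acceptability. The missing control group, which the plan acknowledges, leaves every change score open to time trends, including any added here.

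All of this stands and sets the size of the point. It does not answer why the deficit that B.4 names has no clear place in the variables F.8 tests for two elements. ARME is filed under motivation, not self-image, and the only stated referent for the self-image questionnaire leaves smoking out.

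**Conclusion.** The point holds as a loose fit between rationale and measurement, confined to two of the three elements. The F.8 change test on emotional response and self-image is less sensitive to the smoking-related shift that B.4 argues for, and more exposed to the course of the cancer, than it needs to be. The size of the loss cannot be derived from the documents; the power figures above rest on assumed shares, drifts and a correlation of 0.5.

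Two stronger readings should be resisted. The first is that a null or positive result would say nothing about the booklet. That goes too far, because the existing measures cover part of what the booklet targets, and the difficulty in attributing a positive result comes largely from the uncontrolled design. The second is that the general scales should give way to a single smoking item. That would exchange two published scales for one unvalidated question, which is a debatable trade.

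No sample size change follows, and no progression criterion is affected. It is a cheap improvement to make while the questionnaire is still unwritten.

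**What to change.** **Self-image.** In D.2.3, state that the questionnaire will include, beside the patient items, possible-self items about being a smoker or a non-smoker with cancer, now and in the future, and about how others would see continued smoking. In F.8, name these items as the self-image change variable.

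**Emotional response.** Keep I-PANAS-SF and FAC. Add a brief item or items on feelings about smoking after diagnosis, such as guilt or fear when smoking. Leave the relapse item as it is. In F.8, report the new items separately, next to the validated scales.

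**Cost.** A few extra unvalidated questions at each of the three assessments and a sentence or two in F.8. There are no added visits and no change to N. D.2.3 already accepts purpose-written measures where no validated one exists. The change does not remove time trends, which only a control group could address.

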## D.2.6. Study design considerations.

**D.2.6.1. Selection of cancer types.** We will recruit patients with breast, colorectal, gynecological, skin melanoma, or bladder cancer. In preliminary analyses with our patients at MCC, we found that these were the types of cancer with higher rates of smoking and with generally high 5-year survival rates [64]. Moreover, colorectal, gynecological, and bladder are moderately smoking-related, whereas breast and skin melanoma are not. Thus, we will be able to examine if cessation motivation depends on cancer smoking relatedness. In Study I, we will determine if it is acceptable for our materials related to gynecological cancers to be broad and inclusive of all gynecological cancer types, or if we will need to develop materials by specific disease sites (e.g., cervical, ovarian). If this intervention is successful, it can be extended to other cancer types.

**D.2.6.2. Smoking Motivation vs Cessation Intervention.** We decided to focus on a motivational intervention instead of including an evidence-based smoking cessation intervention because: (1) our preliminary data suggest that cessation motivation is inversely associated with the cancer's smoking-relatedness [15]; thus, by increasing the perceived relevance of patients' smoking to their specific cancer and its treatment, we expect to increase cessation motivation; (2) clinical pragmatism—to proactively reach patients without disrupting their cancer treatment experience or the functioning of the cancer clinics requires an initially brief intervention; and (3) systematic research—because the novelty of this line of research involves its motivational focus on specific cancer types, it is reasonable to focus this initial research effort on that aspect. Motivation for quitting smoking is an essential first step towards smoking cessation.

**D.2.6.3 Study Timeline.** A detailed description of the study timeline has been included in the Form E attachments.

**D.2.7. Future directions.** This study will inform a future RCT. If the intervention meets our a priori criteria with respect to demand, feasibility, and acceptability, we anticipate submitting an R01 to NCI in which the intervention will be combined with an evidence-based smoking cessation intervention and compared against no-treatment and contact-matched comparison conditions in the oncology clinic setting.

## E. PROTECTION OF HUMAN SUBJECTS STUDY I

### E.1. Risks to Human Subjects

### **E.1.1. Human Subjects Involvement, Characteristics, and Design**

In this study, we will conduct a qualitative assessment of representative cancer patients regarding knowledge about their cancer and smoking, and their perceived needs and preferences regarding motivation to quit smoking. This will guide the development of messages and the content of the intervention. Once a full draft of the intervention has been developed, it will be presented to the target population and we will make modifications according to their feedback.

Participants in this study will be 35-45 individuals who recently (i.e., within 3 months) received a diagnosis of breast, colorectal, gynecological, skin melanoma, or bladder cancer at Moffitt Cancer Center. To be eligible for the study, participants must: a) have smoked at least 1 cigarette in the previous month; b) be able to read and write English; c) not currently enrolled in a smoking cessation program; d) be able to give informed consent; and d) have no additional cancer diagnoses. Patients receiving palliative treatment or with distant metastases will be excluded, as participation may be burdensome. Male patients diagnosed with breast cancer will be excluded as lifetime risk for breast cancer in men is very low (less than 1% of breast cancer worldwide).

### **E.1.2. Study Procedures, Materials, and Potential Risks**

This study does not involve any deception. Potential participants will be called over the phone or approached by a trained research assistant and will be screened for eligibility criteria using a brief eligibility screening form. Eligible patients will be asked if they would like to participate in a study of tobacco use by cancer patients. They will be asked to review a consent form and will be provided the opportunity to ask any questions. All subjects will sign consent forms prior to their participation. Informed consent and consenting procedures will adhere to the Advarra Institutional Review Board guidelines. For the participants who complete the study remotely, we will consent them verbally and we will provide them a copy of the informed consent via email or mail and we will request a waiver of documentation of consent from the IRB.

Following the informed consent, participants will complete a baseline questionnaire and will be interviewed for about an hour. The following materials will be used:

- a. Questionnaires measuring sociodemographic characteristics, smoking history and nicotine dependence, perception of smoking relatedness of their cancer, risk perception, affective and emotional response, self-image, and motivation to quit smoking.
- b. Audio-tapes and transcripts of interviews.

Participants may be sharing personal information about themselves during the in-depth interviews. In addition, tobacco smoking for cancer patients may be a sensitive topic due to perceived stigma. Thus, in the event that a patient appears distressed, a social worker will be available to assist with making the appropriate referrals.

## **E.2. Adequacy of Protection Against Risks**

### **E.2.1. Informed Consent and Assent**

Potential participants will be called over the phone or approached by a trained research assistant during a visit to the Moffitt Cancer Center. They will be screened for eligibility criteria using a brief eligibility screening form. Eligible patients will be asked if they would like to participate in a study of tobacco use by cancer patients. If willing to participate they will be escorted to a private room where the research assistant will explain privately the informed consent. Then, they will be asked to review the consent form and will be provided the opportunity to ask any questions. All subjects will sign consent forms prior to their participation. Informed consent and consenting procedures will adhere to the Advarra Institutional Review Board guidelines. Participants not able to provide informed consent will be excluded from the Study. If necessary, this would be completed remotely by mail, email, or the phone.

### **E.2.2. Protections Against Risk**

The potential risks are judged to be minor. We recognize that some patients may experience some discomfort in completing the measures. In the event that a patient appears distressed, a social worker will be available to assist with making the appropriate referrals.

Patients may provide personal information about themselves during the in-depth interviews, as well as on screening or demographic questionnaires. All research staff will receive training in research ethics. Confidentiality will be maintained by using subject numbers on data, rather than subjects' names or their patient IDs to avoid data breach. Subject data will be available only to research staff. Paper data will be kept in locked filing cabinets in locked laboratory rooms; electronic data will be stored on password-protected, secured servers at Moffitt Cancer Center. Identifying information will not be reported.

### **E.3. Potential Benefits of the Proposed Research to Research Participants and Others**

The main benefit to participants is involvement in research that may lead to the development of interventions to help cancer patients to increase their motivation to quit smoking. However, participation may motivate some patients to quit smoking, which has multiple health benefits, particularly for this population.

### **E.4. Importance of the Knowledge to be Gained**

Improved knowledge regarding how to increase smoking cessation motivation in patients with a cancer not widely known to be related to smoking could have dramatic public health implications. The ultimate aim of this study is to motivate patients to eventually quit smoking, which will improve health, quality of life, and survival for these individuals.

